14.0 Withdrawal of Participants*

Participants will be informed that they can choose not to participate in the study. They can skip any questions they do not wish to answer, or withdraw from the study at any time.

15.0 Risks to Participants*

We expect the research-related risk to be minimal: the probability & magnitude of harm/discomfort anticipated in the research is no greater than those ordinarily encountered in daily life or during the performance of routine physical or psychological examinations/tests.

There are no anticipated physical risks of participating in this study. However, participants may experience psychological or emotional distress from participating in the study, particularly activities related to the way their family interacts or communicates about ovarian cancer and genetic risks. Survivors may worry about their family members' emotional distress. Participants whose motivations for study enrollment include histories of ovarian cancer in either themselves or their family members may find it upsetting to re-visit their personal experiences.

There is a small potential risk of outreach to family members of a recently deceased woman. In GCR's past experiences, this event does indeed happen on occasion but the typical response is a family member contacts GCR to inform about the passing of their family member. No adverse event has been reported thus far (e.g., distress, confusion). The proposed research activities present the same outreach risk (which is minimal) as routine contact by the GCR.

Other potential risks to participation include the possibility of a breach of confidentiality or data privacy in which the study participant's involvement in genetic counseling, comments or survey information may become known by individuals not directly involved in the research.

In order to attenuate the likelihood and impact of these potential risks:

Throughout recruitment, GCR will perform monthly checks to minimize the risk of initiating contact with a recently deceased woman. If such contact occurs, GCR's standard protocol is that the registry is the single point of contact for all patient

PROTOCOL TITLE: Testing a Low Cost Population- and Theory-Based Outreach Intervention to Engage Ovarian Cancer Survivors and their Close Relatives to Consider Genetic Services.

outreach. The GCR's primary goal is to ensure that trained registry staff respond to such calls and work to reduce possible distress and address questions and concerns per their standard protocols.

Participants will be informed that their responses will be described in aggregate and they can skip any questions they do not wish to answer, or withdraw from the study at any time. Additionally, all of those who log in to the study website (restricted or expanded) will be provided with a 24-hour call in line (hosted by the GCR Registry) to request contact from the study team regarding any concerns. Jointly, our research team includes 2 board-certified genetic counselors ([name], [name]), an oncologist ([name]) and a bioethicist ([name]) with expertise in areas that may raise concerns for participants. We can arrange call backs to participants who register concerns related to their participation in the study.

Participants who receive tele-genetic counseling will have the opportunity to have their questions/concerns related to genetic screening/testing addressed by the genetic counselors as is standard practice. All of the genetic counselor interns will have to complete at least one cancer rotation at the time of the study and they will receive clinical oversight by senior clinicians including Drs. [name], [name], and [name]. Each of these genetic counseling professionals have extensive experience in cancer genetics. During the online discussions (Aim 3), they will also be available to answer questions related to cancer care and genetic counseling via online written responses.

More detail about data security and participant confidentiality are described below in the Data Management and Monitoring and Confidentiality sections of this protocol.

16.0 Potential Benefits to Participants*

Participants may or may not benefit directly by taking part in this study. Through reviewing the print- and website-based communication materials and undergoing genetic counseling, participants may develop a broader knowledge base, competence and confidence to interpret and analyze genetic risk information related to hereditary cancers. If participants choose to undergo genetic testing in the future and are found to be a mutation carrier of hereditary cancer syndromes, the information will be useful for their personal health care management and for their family members' health as well.

As any risks of participating are anticipated to be minimal, it is believed that the knowledge gained from participants' responses will provide societal benefits that outweigh any risks to the participants.

Results of this study could inform the adaptation of similar traceback programs for other heritable cancers and in other states to increase the likelihood of fair distribution of precision medicine advances.

Data analysis for primary RCT outcomes: We will conduct all analyses in SAS 9.4. Because our sample is identical with the study population, there will be no missing data for the main outcome. We will code people who do not engage in primary study outcomes (e.g., visiting website) as '0', and all others as '1'. Among participants interacting with the website, we will calculate dose of web use as the number of sessions and time spent on the website as indicators of central processing. For the main trial outcomes, we will first examine distributions (frequencies and means/standard deviations) for all relevant variables. To analyze *survivor outcomes*, we will use logistic regression to analyze arm assignment as a predictor of: 1) reach and 2) uptake of genetic counseling yielding an odds ratio and 95% confidence interval for the intervention effect. For *close relatives outcomes*: 1) reach, 2) uptake of B-RST™, and 3) uptake of genetic counseling, we will conduct a logistic multilevel analysis accounting for clustering of close relatives in cancer survivors (i.e. close relatives are level-1 who are nested in level-2). Given the binary nature of the outcomes, we will assess dispersion and adjust for over- or under-dispersion in our analyses. Subsequently, we will conduct moderator analyses to see for whom the intervention worked best. These analyses will entail expanding the described logistic regression/logistic mixed models to include direct effects of a proposed moderator (e.g. age at diagnosis) and an interaction effect between the moderator and arm assignment. Although the main outcomes will have no missing data, our covariates might have missing data. We will assess patterns of missingness and use appropriate methods (i.e. full-information maximum likelihood estimation or multiple imputations) to account for missing data.

Data analysis for post-intervention online survey: To evaluate factors suggested by information processing theories that are associated with the intervention, we will conduct quantitative

PROTOCOL TITLE: Testing a Low Cost Population- and Theory-Based Outreach Intervention to Engage Ovarian Cancer Survivors and their Close Relatives to Consider Genetic Services.

analyses of survey data to characterize participants' processing and demographics. We will apply linear or logistic regression to compare differences on knowledge, comprehension, between the intervention and standard outreach arms. For example, in these analyses we will evaluate whether participants in the MBI arm show higher cancer genetic knowledge than relatives in the standard outreach arm. Overall, we will adjust these analyses for health literacy and age.

User Pattern Analysis: To assess patterns of website use and identify sub-groups of users, we will use traditional web tool user data (e.g. time of access after invite to use, frequency of use) and programmatic user data (e.g. types of viewed content, types of completed tasks). These analyses will be conducted approximately 2/3 of the way through recruitment when we have adequate numbers for characterizing user patterns. We will identify the sub-groups through descriptive analysis and if meaningful using cluster analysis.⁷⁰ Subsequently, we will use multinomial regression analysis to understand sociodemographic differences in cluster members and use the clusters as strata for the recruitment into the online discussion forum described above.

Process Outcome Measures: Implementation reach, dosage, and fidelity is based on proportions and means/standard deviations for relevant quantitative variables (e.g., website access, number of visits/length, counseling session evaluation scores). Outreach approach's acceptability, barriers, facilitators, and perceived alignment with ethical principles will be based on descriptive analyses of *quantitative* survey responses (mail and online – e.g., the proportion of participants who vote "yes or no" and rate outreach as protecting autonomy and respecting family relationship (relational autonomy)). For *qualitative* responses on the online discussion forum, we will conduct qualitative content analysis using MaxQDA. We will identify distinct themes and categories related to each discussion topic, such as acceptability, and alternative contact strategies and best methods of supporting relational autonomy. Two study team members (led by [name]) will independently code five responses per discussion topic to ensure agreement of coding. Using a final codebook, a bioethics fellow and graduate assistants will conduct coding. We will systematically review all responses for the most commonly occurring themes and will identify representative quotes. The recorded counseling sessions (~70) will also be qualitatively coded to compare 4 measures by study arm: 1) session length in minutes, 2) verbal dominance (ratio of counselor to participant statements), 3) patient activation (number of patient medical, psychosocial, and lifestyle statements and questions), and 4) nonverbal affect assessed by a 6-point scale^{71,72} (low to high) reflecting both positive (interest, warmth, engagement, empathy, respectfulness and interaction) and negative affect (dominance and hurried for the genetic counselor, anxiety and distress for the patient).

As described in detail in section 19.0, confidentiality safeguards are in place during the following activities: recruitment, informed consent process, participation in study website, survey and online forum, data transportation, data analysis, and study finding reporting. Only the study ID number will be attached to data. In terms of reporting of study results, only basic sociodemographic identifiers (e.g., age, income, education) will be reported in aggregate.

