B.3. Randomization: We will randomly assign cancer survivors (N=2,918) in a 1:1 ratio to either the MBI arm (n=1,459) or the waitlist standard outreach arm (n=1,459). Given our access to the entire population of ovarian cancer survivors in GA and characteristics of their cancer and treatment, we will use a covariate adaptive randomization procedure.^{43,44} In this procedure, we will randomly assign the first participants to a group, then will assign subsequent participants to a particular group by taking the covariates and previous assignment into account to adapt the probability of group assignment. This approach ensures our randomization is superior to simple randomization that only works perfectly for very large samples.⁴⁵ It will result in a covariance balanced allocation and thus avoid potential influence of covariates on the intervention results. We will use the SAS macro developed by Colavincenzo to execute the randomization.⁴⁶ We will choose covariates we expect are related to reach from the cancer registry data. Examples are year of diagnosis and age at diagnosis. Registry staff will randomize identified survivors to arm using sequentially numbered and sealed envelopes.

B.4. GCR Recruitment Procedures: The proposed recruitment procedures comply with GCR's current standards. We adapted them from strategies that were effective in other studies using cancer registry for recruitment^{34,39,42,47,48} that will allow for sustaining and disseminating the intervention beyond the study. We will classify survivors who log in to the study website as "reached." Recruitment will rely on multiple communications aimed to encourage survivors to log in to the study website with the number of contacts largely identical for both arms (Figure 4).

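### If survivors are allocated adaptively as section B.3 describes, the arm-only model for survivor reach gives no credit for the balance and is mildly conservative

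*Combined protocol and SAP*

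**What the plan says.** Section 6.1, B.3 (Randomization) assigns 1,459 survivors to each arm and states "we will use a covariate adaptive randomization procedure". On the factors it says "We will choose covariates we expect are related to reach from the cancer registry data", and offers year and age at diagnosis as examples. No final list, categories or strength of association is given. The stated purpose is to "avoid potential influence of covariates on the intervention results". The same paragraph ends by having registry staff allocate from numbered, sealed envelopes, and does not explain how that fits with probabilities that adapt to earlier assignments.

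Section 17.0 (Data analysis for primary RCT outcomes) says of survivors: "we will use logistic regression to analyze arm assignment as a predictor of: 1) reach and 2) uptake of genetic counseling". The result of that model is to be reported on the odds-ratio scale with a 95% interval. Covariates come in afterwards, when this model is expanded for moderators, and the moderator named as an example is age at diagnosis, which is also one of the two examples in B.3. Section 17.0 also allows for missing covariate values through "full-information maximum likelihood estimation or multiple imputations", without saying which covariates belong in the primary model. For the post-intervention survey, by contrast, adjustment for health literacy and age is written out.

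**The concern.** Balancing on covariates that predict the outcome removes part of the chance variation between arms. A model with arm alone does not know this. Its standard error still counts the variation that the allocation has taken out, so it is larger than the true sampling error of the estimate. The aim stated in B.3 is met in the design but not credited in the analysis.

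What is at stake is precision on survivor reach. Section 17.0 says the study population is limited to Georgia's ovarian cancer survivors, so a narrower interval cannot be bought with more participants. The covariates are already in the registry.

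The point covers survivor reach only. Table 3 counts survivor uptake among the 656 and 145 who log in. That is a subset formed after randomization, in which balance is not assured.

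**Working it through.** **Inputs from the documents.** n = 1,459 per arm (B.3 and Table 3). Reach p1 = 45% and p0 = 10% (Table 3). 95% interval (section 17.0), from which a two-sided 5% test is inferred. Fallback reach of 20% in the MBI arm (power analysis); its total of 436 matches expected log-ins at 20% and 10% of 1,459, so n stays 1,459 per arm.

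**Assumed.** A normal covariate score X with log-odds SD s = 0.3, 0.6 or 1.0, with intercepts solved so that marginal reach is 45% and 10%.

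**Step 1: the plan's own figure.** The risk difference has SE √[(0.45×0.55 + 0.10×0.90)/1,459] = 0.0152. Then 0.35/0.0152 = 23.0, so power is 1.000. Table 3 states >.99: reproduced.

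**Step 2: arm-only standard error.** The marginal odds ratio is (0.45/0.55)/(0.10/0.90) = 7.36. The variance of its log is 1/(1,459×0.2475) + 1/(1,459×0.09) = 0.002769 + 0.007616 = 0.010385, so SE = 0.102.

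**Step 3: true standard error under balance.** Let m_a = P(reach | X, arm a) and q_a = 1 − p_a. Then

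Var = Σ E[m_a(1−m_a)] / (n(p_a q_a)²) + Var(m1/(p1q1) − m0/(p0q0)) / (2n).

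The arm-only variance exceeds this by Var(m1/(p1q1) + m0/(p0q0))/(2n). That is never negative, so in large samples the arm-only SE cannot be too small.

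For s = 0.6: 0.002558 + 0.007361 + 0.000011 = 0.009930, so SE = 0.0996 and the ratio is 0.1019/0.0996 = 1.023.

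**Step 4: null size of the arm-only 5% test** at common reach 10%: 2[1 − Φ(1.96/√(1−R²))], with R² = 1 − E[m(1−m)]/(pq) = 0.008, 0.033 and 0.092.

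| Assumed SD | 0.3 | 0.6 | 1.0 |
|---|---|---|---|
| Arm-only log-OR SE | 0.102 | 0.102 | 0.102 |
| True SE under balance | 0.101 | 0.100 | 0.096 |
| Arm-only SE too large by | 0.6% | 2.3% | 5.8% |
| 95% CI for OR 7.36, arm only | 6.03–8.99 | 6.03–8.99 | 6.03–8.99 |
| 95% CI, balance credited | 6.04–8.98 | 6.06–8.95 | 6.10–8.89 |
| Null size of arm-only test | 4.9% | 4.6% | 4.0% |
| Same excess at 20% vs 10% | 0.5% | 2.1% | 5.8% |
| Conditional OR, adjusted model | 7.6 | 8.3 | 10.2 |
| Its log-OR SE | 0.103 | 0.106 | 0.114 |

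**Step 5: simulation.** With N = 2,918, two assumed 4-level factors, biased-coin minimisation (assumed 0.8/0.2) and 80,000 runs, the ratio of arm-only SE to empirical SD for the log odds ratio is 1.002, 1.021 and 1.050. Null size is 4.9%, 4.6% and 4.1%. Monte Carlo error is about 0.0025 on the ratios and 0.08 points on size, so at SD 0.3 nothing is distinguishable from 1 and 5%. Under simple randomization the null size is 5.0% throughout, and the risk-difference ratio is 1.001, 0.997 and 1.002, so the conservatism comes from the allocation.

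A second set-up, with two 3-level factors and an odds ratio per level of 1.25 to 3, gives theoretical SE ratios of 1.004 to 1.085.

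**Step 6: does adjustment recover the loss?** A standardised marginal log odds ratio from the adjusted model has simulated, calibrated SEs of about 0.100 and 0.097 at SD 0.6 and 1.0, under balanced and simple allocation alike. This agrees with the true SEs in the table.

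**The case against.** The strongest objection is that the effect is immaterial. The plan reports an odds ratio, and the interval moves only from 6.03–8.99 to 6.10–8.89 even at SD 1.0. An unadjusted primary analysis that holds its level is a legitimate choice. This stands, and it is why the point is one to consider and no more.

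The top of the range is also generous. At SD 1.0, survivors one SD above and one SD below the mean differ by an odds ratio of e² = 7.4, as large as the whole planned intervention effect. Registry variables such as year and age at diagnosis would have to supply that. This stands too.

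The premise may fail. If the envelopes hold a simple list made in advance, there is no conservatism. This stands as a condition on the finding. It does not remove the gain from adjusting, which is about the same either way.

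That the model is arm-only is inferred from silence: section 17.0 does not rule out other predictors. But it adds covariates only in the later moderator step and states adjustment where it wants it, so arm-only is the likelier reading.

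A reader might infer that the primary measure should change to a risk difference. The documents do not call for that. An endpoint defined as a proportion does not make an odds ratio unsuitable, and the standardised odds ratio recovers the precision while keeping the planned measure.

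**Conclusion.** The point holds as a small, conditional loss of precision. If allocation is adaptive as B.3 describes, the arm-only standard error for survivor reach is about 0.6% to 5.8% too large over the assumed range, and the test keeps its level with a null size of 4.0% to 4.9%. At SD 0.3 the effect is negligible. The size rests on assumed covariate strength and the direction does not. Confidence is medium, because neither the covariates nor the working of the allocation is settled.

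A reader might infer that the analysis is invalid, that type I error is inflated, or that the trial is underpowered. None of these follows. The error is on the conservative side, power stays above 0.99, and no conclusion changes at the planned effect. Nor does the result carry over to survivor uptake or to the relatives' outcomes.

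**What to change.** In section 17.0, for survivor reach only, state:

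- The primary logistic model includes arm and the covariates used in the allocation, coded as at allocation.
- The reported effect is the standardised (marginal) odds ratio from that model, with a 95% interval from an influence-function standard error or a bootstrap.
- The arm-only model is a sensitivity analysis. A standardised risk difference may be added as a supporting measure but need not replace the odds ratio.

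This keeps the odds ratio and its marginal target (7.36 at the planned rates), with a log-OR SE of about 0.101, 0.100 or 0.096 in place of 0.102. The coefficient odds ratio from the adjusted model should not be the headline: it is conditional, and its SE is larger than the arm-only one.

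The wording needs the covariates and their levels to be fixed in B.3, which should also say how the envelopes fit with adaptive assignment.

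Cost: a few sentences and a little more analysis code. No new data.

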18.0 Provisions to Monitor the Data to Ensure the Safety of Participants*

- N/A. Our project involves no more than minimal risk to participants.

19.0 Provisions to Protect the Privacy Interests of Participants and Confidentiality of Participants' identifiable data

To protect participants' privacy, the community working groups will take place in private settings (e.g., conference rooms). Participants in the telegenetic counseling sessions will be asked to schedule a time when they can speak privately. The online survey and discussion forum will be hosted by the study website and access will be password controlled. We will advise participants to use a pseudonym to maintain their anonymity. Participants can share their responses to the research team only, or make the responses available for other participants to view.

Based on existing best practices for security and privacy in health information technology, we have employed the technologies and features needed to ensure privacy and security of personal information. These features address identity and access management, secure storage, secure messaging, encryption, and other security technologies and approaches. The GCR logistical survivor contact records on mail-outs and phone calls (i.e., messages left, call-backs) will be managed in accordance with HIPAA Privacy Rule, 45 CFR Parts 160 and 164. All other data (i.e., website login and user-pattern data, telegenetic counseling logbook, online survey and discussion forums) will be collected via HIPAA compliant online platforms developed and managed by Peachtree Solutions. All of the data will then be downloaded to Emory password protected, research network drives.

Peachtree solutions has three levels of safeguards built into their business approach: administrative, technical and physical to insure the security and privacy of sensitive data. Administrative safeguards include annual risk assessments of the hosting environment and coding practices. Employees are trained annually on the proper handling of sensitive client data and secure coding techniques. Policies and procedures are reviewed on an annual basis and reviewed by an outside security department on a regular basis as a normal course of business. All employees are background checked at the time of hire. Technical safeguards include quarterly external vulnerability scanning, and access controls (e.g., unique user identification; emergency access procedures, automatic logoff, authentication, and encryption/decryption). Physical safeguards include contingency procedures for facility access in support of data restoration under the disaster recovery and emergency operations plan. All data is stored in an ISO 9001 certified facility that requires badge and biometric confirmation to gain access to the data center floor. All data is stored in a locked server cabinet that only datacenter employees can access. Access is logged. Policies and procedures are implemented toward final disposition of PHI that is stored. All data is backed up every 3 hours and stored both locally and in a remote data center using hard encryption.

Strict confidentiality of the completed data will be maintained. A unique random identification number will be generated and assigned to each participants. These identification numbers will be used for all data analysis and kept separately from identifying information and accessible only by the study team. Identifying information collected for participant recruitment (patient contact

lists, phone numbers) will be transferred and stored using secure, encrypted file transfer protocols. Encryption will be used for all data in transit between the web browser and the server, all identifiable data at rest in the database, and all backups of the data. Access to decrypted identifiable data will be limited to a need-to-know basis for study team members. Any data collected for research will have identifiable data removed from the data set. All administrative accounts will have their own unique login (no shared logins). All data will be secured in password-protected computer files and reported at the group or aggregate level. Names will not be identified in any reports resulting from the research, and no individual information will be released to anyone outside of the project. Study personnel will be required to have IRB authorization which requires ongoing credentialing regarding procedures to maintain confidentiality. Research staff will also sign statements of confidentiality. Only necessary study personnel will have access to any of these files. Identifying information (phone numbers) will be deleted from all files at the end of the study period. Names will not be identified in any reports resulting from the research, and no individual information will be released to anyone outside of the project. Study personnel will be trained regarding procedures to maintain confidentiality. Research staff will also sign statements of confidentiality. Access to subject personal identifiers will be restricted to the PI, recruitment staff, and upon written request, to the Institutional Review Board or other appropriate regulatory agencies. Identifying information (phone numbers) will be deleted from all files at the end of the study period.

The data and safety monitoring will be conducted annually by an independent data safety monitoring committee. The data will be reviewed include: adverse events, enrollment numbers, raw data, and outcomes. Safety monitoring results will be reported to the IRB of the Rollins School of Public Health of Emory University.

All study team members have current CITI certifications through Emory University. Study team members' preparedness will be enhanced and accomplished by pretrial and ongoing training on basic breast cancer and hereditary cancer risk information, study protocol, and ethical conduct. In addition, the study team will also receive training in how to refer participants to informational and support resources, including patient navigator programs in the survivor's locale that can assist in additional medical care needs.

